### **Individual PK Parameter Rules**

- Only quantifiable concentrations will be used to calculate PK parameters with the exception of special handling of certain concentrations reported below the lower limit of quantitation (BQL). Plasma concentrations reported as BQL will be set to a value of zero when all of the following conditions are met:
  - The compound is non-endogenous.
  - The samples are from the initial dose period for a subject or from a subsequent dose period following a suitable wash-out period.
  - The time points occur before the first quantifiable concentration.
- All other BQL concentrations that do not meet the above criteria will be set to missing.
- Also, where two or more consecutive concentrations are BQL towards the end of a profile, the profile will be deemed to have terminated and therefore any further quantifiable concentrations will be set to missing for the calculation of the PK parameters unless it is considered to be a true characteristic of the profile of the drug.

### **Individual Concentration vs. Time Profiles**

- Individual concentrations will be plotted utilizing actual sampling times.
- The terminal point selections will be indicated on a semi-logarithmic plot.

### **Average Concentration vs. Time Profiles**

- The average concentration profiles will be graphed using scheduled (nominal) sampling times.
- The average concentration profiles will be graphed using arithmetic average concentrations.
- The pre-dose average concentration for single-dose data from non-endogenous compounds will be set to zero. Otherwise, only quantifiable concentrations will be used to calculate average concentrations.
- Concentrations at a sampling time exceeding the sampling time window specified in the protocol, or  $\pm 10\%$ , will be excluded from the average concentration profiles.
- Concentrations excluded from the mean calculation will be documented in the final study report.

- A concentration average will be plotted for a given sampling time only if 2/3 of the individual data at the time point have quantifiable measurements that are within the sampling time window specified in the protocol or  $\pm 10\%$ . An average concentration estimated with less than 2/3 but more than 3 data points may be displayed on the mean concentration plot if determined to be appropriate and will be documented within the final study report.

### **Treatment of Outliers during Pharmacokinetic Analysis**

Application of this procedure to all PK analyses is not a requirement. Rather, this procedure provides justification for exclusion of data when scientifically appropriate. This procedure describes the methodology for identifying an individual value as an outlier for potential exclusion, but does not require that the value be excluded from analysis. The following methodology will not be used to exclude complete profiles from analysis.

#### Data within an Individual Profile

A value within an individual profile may be excluded from analysis if any of the following criteria are met:

- For PK profiles during multiple dosing, the concentration of the pre-dose sample exceeds all measured concentrations for that individual in the subsequent post-dose samples.
- For PK profiles during single dosing of non-endogenous compounds, the concentration in a pre-dose sample is quantifiable.
- For any questionable datum that does not satisfy the above criteria, the profile will be evaluated and results reported with and without the suspected datum.

#### Data between Individual Profiles

1. If  $n < 6$ , then the dataset is too small to conduct a reliable range test. Data will be analyzed with and without the atypical value, and both sets of results will be reported.
2. If  $n \geq 6$ , then an objective outlier test will be used to compare the atypical value to other values included in that calculation:
  - a. Transform all values in the calculation to the logarithmic domain.
  - b. Find the most extreme value from the arithmetic mean of the log transformed values and exclude that value from the dataset.
  - c. Calculate the lower and upper bounds of the range defined by the arithmetic mean  $\pm 3*SD$  of the remaining log-transformed values.
  - d. If the extreme value is within the range of arithmetic mean  $\pm 3*SD$ , then it is not an outlier and will be retained in the dataset.

---

- e. If the extreme value is outside the range of arithmetic mean  $\pm 3*SD$ , then it is an outlier and will be excluded from analysis.

If the remaining dataset contains another atypical datum suspected to be an outlier and  $n \geq 6$  following the exclusion, then repeat step 2 above. This evaluation may be repeated as many times as necessary, excluding only one suspected outlier in each iteration, until all data remaining in the dataset fall within the range of arithmetic mean  $\pm 3*SD$  of the log-transformed values.

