## 5. STUDY DESIGN

This study is a Phase 1, investigator- and subject-blinded, randomized, placebo-controlled study in healthy Chinese subjects.

Subjects will be enrolled into 1 of 3 cohorts and receive single and multiple doses of lasmiditan or placebo in a parallel design. Each cohort will comprise 12 subjects (10 lasmiditan: 2 placebo) and will be assigned the following doses:

- Cohort 1 = 50 mg lasmiditan (or placebo)
- Cohort 2 = 100 mg lasmiditan (or placebo)
- Cohort 3 = 200 mg lasmiditan (or placebo)

Subjects will be evaluated for study eligibility  $\leq 28$  days prior to enrollment. Subjects who fulfil the eligibility criteria will be admitted to the clinical research unit (CRU) on Day -1 (the day before their first dose of lasmiditan or placebo).

After randomization on Day 1, investigational product (IP: lasmiditan or placebo) will be administered orally once on the morning of Day 1 after an overnight fast of at least 8 hours. Following a period of at least 72 hours without IP dosing, subjects will receive multiple once-daily oral doses of IP on Days 4 to 10 (7 days of dosing), after overnight fasts of at least 8 hours prior to each dose. The doses of lasmiditan administered on Days 4 to 10 will be the same dose as that administered on Day 1 for each subject.

Subjects will be discharged from the CRU on Day 12 following completion of all scheduled procedures and will attend a follow-up visit approximately 7 to 10 days following final oral dose of IP.

The planned study duration for each subject will be up to 50 days.

Blood samples will be collected for PK analysis. Safety and tolerability will be assessed throughout the study by means of adverse event (AE) review, physical examinations, vital sign measurements, 12-lead electrocardiograms (ECGs), clinical laboratory tests, and Columbia-Suicide Severity Rating Scale (C-SSRS).

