### **9.3.2 Pharmacokinetic Statistical Methodology**

All PK parameters will be summarized by analyte and treatment, and listed. Plots of mean (+/- SD) plasma concentrations by analyte and treatment over time will be presented.

Pharmacokinetic parameters for lasmiditan will be evaluated to estimate dose proportionality over the 50 to 200-mg dose range on Day 1 and Day 10 separately and will be presented graphically, as well as in analysis tables. Log-transformed  $C_{max}$  and AUC parameters ( $AUC[0-\infty]$  for Day 1 and  $AUC\tau$  for Day 10) will be evaluated using a power model (where the log of the dose will be an explanatory variable) to estimate ratios of dose-normalized geometric means and the corresponding 90% confidence intervals (CIs). The estimated ratio between the highest and lowest doses will be used to assess dose proportionality. The intersubject coefficient of variation will be derived.

Example SAS code:

```
proc mixed data=pk01;  
  by param pkday;  
  title1 j=c "Estimate of slope";  
  model log_pk = log_dose / solution residual cl alpha=0.1;  
  estimate 'xx mg' intercept 1 log_dose yy / alpha=0.1 cl; /*Log value  
  of xx*/  
  estimate 'zz mg - xx mg' log_dose pp / alpha=0.1 cl; /*Difference in  
  log values of zz and xx*/  
  ods output estimates=estims;  
  ods output solutionf=doseprop;  
run;
```

Additional analysis will be performed if warranted upon review of the data.

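### The between-profile outlier test uses a fixed 3 SD limit that is not scaled to 8-10 subjects: it flags a genuine value in about 22-25% of clean dose groups, and 90% CI coverage falls to about 85% if every flag is excluded

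*SAP*

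**What the plan says.** The rule is in SAP 9.3.1, under the heading on data between individual profiles. With fewer than six values, no test is run and results are reported with and without the atypical value. With six or more, the steps on the log scale are:

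- "Find the most extreme value from the arithmetic mean of the log transformed values and exclude that value from the dataset";
- "Calculate the lower and upper bounds of the range defined by the arithmetic mean" plus or minus 3 SD of the values that remain;
- if the value lies inside, keep it; if outside, "then it is an outlier and will be excluded from analysis".

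Provided at least six values remain, "This evaluation may be repeated as many times as necessary, excluding only one suspected outlier in each iteration". Reporting both ways is not required in this branch.

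The introduction to the outlier procedure is softer. It says that the procedure need not be applied to all PK analyses, and that it identifies a value for possible exclusion but "does not require that the value be excluded from analysis". Excluded values must be documented in the final report.

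The lasmiditan groups have 10 subjects each by design (SAP 5), with about 8 completers sought (SAP 7). SAP 9.3.2 fits a power model to log Cmax and log AUC, separately for Day 1 and Day 10, and reports 90% CIs. It adds: "The intersubject coefficient of variation will be derived".

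**The concern.** Three SD is a rare distance for one value chosen in advance and judged against a known SD. Here the value is chosen because it is the most extreme of n, and the SD is estimated from only 7 to 9 others, without the value under test. At these sizes 3 SD is an ordinary distance for a genuine extreme. The SAP accepts that sample size matters when it declines to test below six, but it makes no allowance for n from six upwards.

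Removing genuine extremes pushes in one direction: residual variance and the intersubject CV are biased down and the CI is too narrow. PK in Chinese subjects is the primary objective, and the protocol (5.4) wants these data for judging ethnic sensitivity, so between-subject spread is a result in its own right.

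**Working it through.** Neither document states a false-flag rate or a coverage after exclusion, so there is no plan figure to reproduce.

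**Inputs.** Multiplier 3, applied to the SD of the other n-1 log values (SAP 9.3.1); n = 8 to 10 per dose group (SAP 5 and 7); doses 50, 100 and 200 mg; power model with two-sided 90% CI (SAP 9.3.2). Assumption: log values are normal with no true outliers.

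**1. False-flag rate per group.** For any one value, its distance from the mean of the others, divided by (SD of the others × √(1 + 1/(n-1))), follows t with n-2 df. Hence

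P(flag) ≈ n × P(|t| with n-2 df > 3/√(1 + 1/(n-1))).

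| n | 3/√(1+1/(n-1)) | two-sided P | n × P | simulated |
|---|---|---|---|---|
| 8 | 2.806 | 0.0309 | 24.7% | 24.7% |
| 9 | 2.828 | 0.0255 | 22.9% | 22.9% |
| 10 | 2.846 | 0.0216 | 21.6% | 21.7% |

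The formula is an upper bound; 1,000,000 simulated groups per n show that it is practically exact here.

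**2. Any of three dose groups, per parameter and day.** 1 - (1 - 0.247)³ = 57% at n = 8; 1 - (1 - 0.216)³ = 52% at n = 10.

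**3. Coverage under full application.** Trials were simulated with exact dose proportionality. Each dose group was screened, the test was repeated while at least six values remained, every flagged value was dropped, and the power model was fitted. Coverage does not depend on the CV, and it is the same for the slope and for the 200/50 ratio.

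| n per group | coverage, no exclusion | coverage, 3 SD rule | residual variance / true | CI width / full-data width |
|---|---|---|---|---|
| 8 | 90.0% | 84.8% | 0.86 | 0.95 |
| 9 | 90.1% | 85.4% | 0.88 | 0.95 |
| 10 | 90.0% | 85.5% | 0.89 | 0.95 |

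With a single pass instead of repeats, coverage is 85.1% (n = 8) and 85.9% (n = 10).

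For the CV, the documents give no value. Taking 40% as an illustration, the log variance is ln(1 + 0.40²) = 0.148. Multiplying by 0.86 or 0.89 and converting back gives a reported CV of 36.9% or 37.6%.

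**4. Coverage under other readings.**

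- Half of the flagged values excluded: 87.7% (n = 8), 88.2% (n = 10).
- Test run on pooled power-model residuals (24 or 30 values): some value flagged in 18-19% of analyses, coverage 87-88%.
- Test run on undivided log values across all doses (CV 30-40%): some value flagged in 0.4-2.5% of analyses, coverage 89.2-89.9%, against 89.5-90.6% without the rule in the same runs.

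**5. A limit scaled to n.** Multiplier = t(1 - α/(2n), n-2) × √(1 + 1/(n-1)). At α = 5%: 4.115 × 1.069 = 4.40 (n = 8); 3.947 × 1.061 = 4.19 (n = 9); 3.833 × 1.054 = 4.04 (n = 10). Under full application coverage is then about 88.5-89%.

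Detection of one value truly shifted by 5 SD:

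| n | 3 SD | α = 5% | α = 1% |
|---|---|---|---|
| 8 | 94% | 69% | 35% |
| 10 | 95% | 77% | 47% |

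The α = 1% multipliers are 6.10 at n = 8 and 5.31 at n = 10.

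**The case against.** The strongest reply is that the SAP does not order a screen of every group. The test is aimed at a value already thought atypical, and both its use and the exclusion are left to judgement. The comparison set is described only as the other values in the same calculation; for the power model that could mean all 24-30 values, and on that reading the effect runs from modest to negligible. This stands. A reader might infer from the rule that the trial's 90% CIs will cover only 85%. The documents do not support that, because 85% needs screening within each dose group and exclusion of every flag.

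Two further points stand in part. The effect is moderate: the interval narrows by about 5%, and the CV bias of about 2.5-3 points is roughly half the sampling error of a CV on 22-28 df (about 5-6 points). Also, the plan sets no acceptance limit for the 200/50 ratio and no hypothesis test, so no formal decision turns on 85% against 90%. Exclusions must also be documented.

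What does not stand is that discretion cures the limit. The exclusion step is worded as mandatory once a value falls outside, and the procedure is offered as justification for dropping data. A test that fires in more than one clean group in five is weak justification. Documentation does not widen an interval that is too narrow.

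**Conclusion.** The concern holds in a conditional form. The fixed limit is miscalibrated for groups of 8-10. When a clean log-normal group is tested, a genuine value is flagged in about 22-25% of cases, whatever is then done with it.

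The consequence for the reported results depends on use. Coverage of the 90% CI is about 85%, with residual variance down by 11-14%, if every dose group is screened and every flag is excluded as the exclusion step says. It is about 87-88.5% with half the flags excluded or with testing on pooled residuals, and close to 90% if the test is seldom invoked. The SAP does not settle which of these applies. All figures assume log-normal data without true outliers.

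It is also tempting to conclude that only a very strict limit, such as one with a 1% false-flag rate, will do. Nothing in the documents supports that level, and it would miss more than half of true 5 SD shifts. The matter is worth correcting before analysis because the correction is short and the bias runs in one direction.

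**What to change.** In step 2c, replace the fixed 3 with t(1 - α/(2n), n-2) × √(1 + 1/(n-1)), recomputed at each repeat, and state α in advance. With α = 5% the limit is 4.40 SD at n = 8, 4.19 at n = 9 and 4.04 at n = 10. Because the formula needs n, the step should also name the comparison set; these examples take the dose group.

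For n of six or more, also report the power-model ratio, its 90% CI and the intersubject CV with all values included, beside any result with exclusions. The SAP already reports both ways below six. This shows any narrowing, whichever multiplier is used.

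The cost is lower sensitivity: a true 5 SD shift is caught in about 69-77% of groups instead of about 94%. Because the limit rises as n falls, reaching 5.31 SD at n = 6, repeated exclusions also become harder. A value with a documented dosing, sampling or assay cause can still be handled on that ground. Otherwise the change needs a short edit to the SAP and one extra set of outputs.

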#### Reporting of Excluded Values

Individual values excluded as outliers will be documented in the final report. Approval of the final report will connote approval of the exclusion.

### **9.3.2 Pharmacokinetic Statistical Methodology**

All PK parameters will be summarized by analyte and treatment, and listed. Plots of mean (+/- SD) plasma concentrations by analyte and treatment over time will be presented.

Pharmacokinetic parameters for lasmiditan will be evaluated to estimate dose proportionality over the 50 to 200-mg dose range on Day 1 and Day 10 separately and will be presented graphically, as well as in analysis tables. Log-transformed  $C_{max}$  and AUC parameters ( $AUC[0-\infty]$  for Day 1 and  $AUC\tau$  for Day 10) will be evaluated using a power model (where the log of the dose will be an explanatory variable) to estimate ratios of dose-normalized geometric means and the corresponding 90% confidence intervals (CIs). The estimated ratio between the highest and lowest doses will be used to assess dose proportionality. The intersubject coefficient of variation will be derived.

Example SAS code:

```
proc mixed data=pk01;  
  by param pkday;  
  title1 j=c "Estimate of slope";  
  model log_pk = log_dose / solution residual cl alpha=0.1;  
  estimate 'xx mg' intercept 1 log_dose yy / alpha=0.1 cl; /*Log value  
  of xx*/  
  estimate 'zz mg - xx mg' log_dose pp / alpha=0.1 cl; /*Difference in  
  log values of zz and xx*/  
  ods output estimates=estims;  
  ods output solutionf=doseprop;  
run;
```

Additional analysis will be performed if warranted upon review of the data.

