## 9. STATISTICAL METHODOLOGY

### 9.1 General

Data listings will be provided for all data that is databased. Summary statistics and statistical analysis will only be presented for data where detailed in this SAP. For continuous data, summary statistics will include the arithmetic mean, arithmetic standard deviation (SD), median, min, max and N; for log-normal data (e.g. the PK parameters: area under the concentration versus time curves [AUCs] and the maximum observed drug concentration [ $C_{max}$ ]) the geometric mean and geometric coefficient of variation (CV%) will also be presented. For categorical data, frequency count and percentages will be presented. Data listings will be provided for all subjects up to the point of withdrawal, with any subjects excluded from the relevant population highlighted. Summary statistics and statistical analyses will generally only be performed for subjects included in the relevant analysis population. For the calculation of summary statistics and statistical analysis, unrounded data will be used.

Mean change from baseline is the mean of all individual subjects' change from baseline values. Each individual change from baseline will be calculated by subtracting the individual subject's baseline value from the value at the timepoint. The individual subject's change from baseline values will be used to calculate the mean change from baseline using a SAS procedure such as Proc Univariate.

Data analysis will be performed using SAS® Version 9.4 or greater.

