## 9.3 Pharmacokinetic Assessment

### 9.3.1 Pharmacokinetic Analysis

Pharmacokinetic (PK) parameter estimates will be determined using non-compartmental procedures in a validated software program (Phoenix WinNonlin Version 6.4 or later).

Plasma concentrations of lasmiditan (LY573144) and its metabolites (M7, M8, [S,R]-M18 and [S,S]-M18) will be used to determine the following PK parameters for single and multiple dose (unless otherwise specified), when possible:

Parameter	Units	Definition
$C_{\max}$	ng/mL	maximum observed drug concentration
$t_{\max}$	h	time of maximum observed drug concentration
$AUC_{\tau}$	ng.h/mL	area under the concentration versus time curve during one dosing interval (i.e. 24 h)
$AUC(0-t_{\text{last}})$	ng.h/mL	area under the concentration versus time curve from time zero to time $t$ , where $t$ is the last time point with a measurable concentration
$AUC(0-\infty)$	ng.h/mL	area under the concentration versus time curve from time zero to infinity (after single dose only)
$\%AUC(t_{\text{last}}-\infty)$	%	percentage of $AUC(0-\infty)$ extrapolated (after single dose only)
$t_{1/2}$	h	half-life associated with the terminal rate constant ( $\lambda_z$ ) in non-compartmental analysis
CL/F	L/h	apparent total body clearance of drug calculated after extra-vascular administration (LY573144 only)
$V_z/F$	L	apparent volume of distribution during the terminal phase after extra-vascular administration (LY573144 only)
$R_A$		accumulation ratio (based on $C_{\max}$ and $AUC_{\tau}$ ) (after multiple dose only - LY573144 only)
RI		linearity ratio between $AUC_{\tau}$ after multiple dosing day and $AUC(0-\infty)$ after single dosing day (LY573144 only)
MR		metabolic ratio a (after multiple dose only)

a no molar correction will be applied since the metabolites are very similar in molecular weight and within 5% of the molecular weight for lasmiditan.

Trough concentrations of lasmiditan and its metabolites will be evaluated graphically and descriptively for achievement of steady-state. No formal analysis will be performed for attainment of steady-state.

Additional PK parameters may be calculated, as appropriate. The software and version used for the final analyses will be specified in the clinical study report. Any exceptions or special handling of data will be clearly documented within the final study report.

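### Does the example SAS code in SAP 9.3.2 return a raw dose ratio where the text promises a dose-normalised one?

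*SAP*

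**What the plan says.** SAP 9.3.2 plans a power model for log-transformed lasmiditan Cmax and AUC, with Day 1 and Day 10 analysed separately, "to estimate ratios of dose-normalized geometric means and the corresponding 90% confidence intervals (CIs"). It continues: "The estimated ratio between the highest and lowest doses will be used to assess dose proportionality". The protocol describes the same target in its Synopsis and in 10.3.2.2.

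Under the label "Example SAS code" the SAP gives a PROC MIXED fragment. Its model line is "model log_pk = log_dose / solution residual cl alpha=0.1" and its contrast line is "estimate 'zz mg - xx mg' log_dose pp / alpha=0.1 cl". A comment explains that pp is the difference between the two log doses. The fragment ends by sending the estimates to output datasets. It does not say how log_pk is built, and it does not exponentiate anything.

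SAP 9.3.1 says plasma concentrations "will be used to determine the following PK parameters for single and multiple dose" and tabulates those parameters, with Cmax in ng/mL and AUC in ng.h/mL. No dose-normalised parameter is in the table, but the section adds: "Additional PK parameters may be calculated, as appropriate".

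**The concern.** The natural reading of log-transformed Cmax and AUC is the log of the parameter as measured. On that reading the contrast line returns the log of a raw exposure ratio. If a programmer exponentiates it and prints it under a dose-normalised label, a drug with perfectly proportional kinetics shows a ratio of 4 where the reader expects 1. Neither document states the division by dose that would close the gap.

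The affected quantity is the one named for judging dose proportionality, and this is the only inferential analysis planned: SAP 9.4.8 plans none for safety, and SAP 9.3.1 plans no formal test of steady state. A mislabelled ratio could be read as gross departure from proportionality.

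**Working it through.** The documents state no numerical result for this analysis, so there is no figure to reproduce. The check is the algebra of the model.

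**Inputs.** Doses are 50, 100 and 200 mg, with 10 lasmiditan subjects per cohort (SAP 5) and about 8 expected to complete (SAP 7). Intervals are two-sided 90% (alpha=0.1 in the code). pp = ln(200) - ln(50) = ln(4) = 1.3863. The documents give no intersubject CV, so the CVs below are assumptions.

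**Reading A: log_pk = ln(parameter).** The model is ln(PK) = a + b ln(dose). The contrast returns b × 1.3863, and exponentiating gives 4^b. The promised quantity is (GM200/200)/(GM50/50) = 4^b/4 = 4^(b-1).

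| slope b | line exponentiated, 4^b | dose-normalised ratio, 4^(b-1) | quotient |
|---|---|---|---|
| 0.9 | 3.48 | 0.87 | 4.00 |
| 1.0 | 4.00 | 1.00 | 4.00 |
| 1.1 | 4.59 | 1.15 | 4.00 |

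**Reading B: log_pk = ln(parameter/dose).** Subtracting ln(dose) from the response lowers the slope by exactly 1 and leaves every residual unchanged. The same contrast line then returns (b-1) × 1.3863, which exponentiates to 4^(b-1), the promised ratio. The printed slope is b-1, with reference value 0 in place of 1.

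**Confidence interval.** With n per dose at three doses equally spaced on the log scale, SE(b) = s/sqrt(2n(ln 2)^2), where s = sqrt(ln(1 + CV^2)) and df = 3n - 2. For n = 10 and CV 30%, s = 0.2936, SE = 0.0947 and t(0.95, 28) = 1.701. At b = 1 the slope interval is 0.839 to 1.161. Exponentiating limit × 1.3863 gives 3.20 to 5.00, and dividing by 4 gives 0.80 to 1.25. The upper limit over the lower is 1.56 both times.

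| n per dose, CV | raw ratio, 90% CI | dose-normalised ratio, 90% CI |
|---|---|---|
| 10, 20% | 3.44 to 4.65 | 0.86 to 1.16 |
| 10, 30% | 3.20 to 5.00 | 0.80 to 1.25 |
| 10, 40% | 2.98 to 5.36 | 0.75 to 1.34 |
| 8, 30% | 3.11 to 5.15 | 0.78 to 1.29 |

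Every pair is the same interval shifted by ln(4) on the log scale. Precision, residual variance and hence the intersubject CV do not depend on the reading. The code also outputs the slope with its 90% interval, and the dose-normalised ratio is a one-to-one function of the slope, so either reading can be recovered from the other.

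**The case for a change.** The best case for a change is that the example is the only operational description of this analysis in the documents supplied. SAP 3 says the SAP supersedes the protocol's statistical considerations and, with the table shells, serves as the template for the study report. The prose points to an unadjusted response: it speaks of log-transformed Cmax and AUC, the parameter table has no dose-normalised entry, and SAP 9.1 warns: "Summary statistics and statistical analysis will only be presented for data where detailed in this SAP". Reading B does not fully close the gap either, because the slope's reference value then moves from 1 to 0 and the SAP does not say which applies. The remedy would cost one sentence.

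Some of this stands. log_pk is undefined, no division by dose is written down, and Reading A is the more natural one.

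It does not show a wrong rule. The fragment uses placeholders and stops at the output datasets. It contains no antilog, so as printed it yields no ratio of any kind. Later processing must follow, and dividing by the dose ratio belongs in that step. The absence of the division is no more evidence of error than the absence of the exponentiation. The restriction in SAP 9.1 does not count against dose normalisation, because SAP 9.3.2 itself details dose-normalised geometric means. The parameter table describes the noncompartmental output and does not describe how the SAS analysis dataset is built.

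**Conclusion.** No change to the plan follows. The algebra is right: on the unadjusted reading the example line and the named ratio differ by exactly 4 for 200 versus 50 mg (and by 2 for adjacent doses). But the governing text names the dose-normalised ratio clearly and consistently, and a programmer working to it either divides the parameter by dose beforehand or divides the back-transformed estimate and limits by the dose ratio afterwards. Both routes give 4^(b-1).

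The stakes are also small. A ratio near 4 across a fourfold dose range would probably be noticed. The slope and its interval are valid under either definition once the matching reference value is used. Dose proportionality is not itself a listed objective (protocol 4, SAP 4), no acceptance range is set for the ratio, and SAP 7 says the study is not powered for hypothesis testing. A constant factor therefore cannot change a planned decision.

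This conclusion rests on the analyst following the stated target and not simply exponentiating the example line. The table shells, which SAP 3 describes as a separate document, were not available and may already settle the labelling. The interval widths shown depend on assumed CVs of 20% to 40%; the factor of 4 does not.
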